9.5. Reporting of Other Information – Unanticipated Problems

As outlined by the Office for Human Research Protection (OHRP), unanticipated problems must be reported to the IRB according to the requirements of 45 CFR Part 46. Unanticipated problems are considered to include any incident, experience, or outcome that meets **ALL** of the following criteria:

- Unexpected (in terms of nature, severity, or frequency) given:
 - Procedures that are described in the study-related documents, such as the IRB approved research protocol and informed consent document.
 - The characteristics of the subject population being entered into the study.
- Related or possibly related to participation in the study which means there is a reasonable possibility that the incident, experience, or outcome may have been caused by the sample collection.
- Suggests that the study places subjects or others at a greater risk of harm (including physical, psychological, economic, or social harm) than was previously known or recognized.

An incidence, experience, or outcome that meets the three criteria above generally will warrant consideration of substantive changes in the study or informed consent process/document or other corrective actions in order to protect the safety, welfare, or rights of subjects or others. Only a small subset of AEs occurring in human subjects participating in a clinical study will meet these three criteria for an unanticipated problem. There are other types of incidents, experiences, and outcomes that occur during the conduct of clinical study that represent unanticipated problems but are not considered AEs. For example, some unanticipated problems involve social or economic harm instead of the physical or psychological harm associated with AEs. In other cases, unanticipated problems place subjects or others at increased risk of harm, but no harm occurs.

The investigator should promptly notify the IRB when an unanticipated problem involving risks to subjects or others is identified. Also, the investigator should notify Emergent and IQVIA of unanticipated problem(s).

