9.3. Immediately Reportable Events

9.3.1. Principal Investigator’s Reporting Requirements

The following events must be reported via email immediately (eg, within 24 hours of awareness) by the PI or designee to Emergent’s Global Pharmacovigilance Department (Global PV):

- Any SAE regardless of causal association with the IP
- Any potential AESI, eg, AE of autoimmune etiology (refer to the list of AESI terms in [Appendix B](#)) regardless of causal association with the IP
- Any pregnancy where conception occurred after first exposure to the IP through Month 13

The appropriate form (listed below) will be completed and sent by email to the following address:

For SAEs and AESIs, the Serious Adverse Event and/or Adverse Event of Special Interest Report Form will be completed (abbreviated hereafter SAE Report Form, AESI Report Form). Note that the SAE and AESI report forms are not the same as the AE eCRF. Accompanying the form(s) will be source documentation or medical records (eg, discharge summary for hospitalizations, lab reports) which support a diagnosis. Participant identifiers (eg, name, address, telephone number, social security number, medical record number, or hospital/laboratory number) must be redacted from the source documentation.

All SAEs that are unexpected (eg, adverse drug reactions) must be reported to the IRB/IEC as required by ICH GCP E6.

Confirmed pregnancies where conception occurred after first exposure to the IP through Month 13 will be reported to Global PV using the Pregnancy Notification Form. Although normal pregnancy is not an AE, it will mandate discontinuation of IP (refer to [Section 9.4](#)).

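### Section 9.5 ties an unanticipated problem to the sample collection, so prompt IRB notice of non-serious problems caused by the study vaccines is not secured

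*Protocol*

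**What the plan says.** Protocol Section 9.5 states that "unanticipated problems must be reported to the IRB according to the requirements of 45 CFR Part 46". It describes such a problem as "any incident, experience, or outcome that meets ALL of the following criteria". Three criteria follow: the event is unexpected, it is related to the study, and it suggests a greater risk of harm than was known before.

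The relatedness criterion has two halves. It opens with "Related or possibly related to participation in the study which means" and then completes the definition with "there is a reasonable possibility that the incident, experience, or outcome may have been caused by the sample collection".

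The section attaches duties to the definition. "The investigator should promptly notify the IRB when an unanticipated problem involving risks to subjects or others is identified", and the sponsor and the CRO should also be told. The section expects some adverse events to qualify: "Only a small subset of AEs occurring in human subjects participating in a clinical study will meet these three criteria for an unanticipated problem".

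Section 9.3.1 gives a separate route to the IRB: "All SAEs that are unexpected (eg, adverse drug reactions) must be reported to the IRB/IEC as required by ICH GCP E6".

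**The concern.** The two halves of the relatedness criterion do not have the same scope. Participation in this study means up to three injections, blinded allocation, an e-diary, follow-up calls and data handling, as well as blood and urine sampling. The defining half keeps only the sampling. Because the criteria are joint, the narrower half controls the result.

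This is an operative reporting rule that about 40 sites are to apply. A site that follows the printed words could properly conclude that an unexpected problem caused by a vaccine lot, an injection or a lapse in study conduct is not an unanticipated problem. Sites that rely on the opening words would conclude the opposite. At stake is whether the IRB hears promptly about problems that may call for a change to the study or the consent form.

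**Working it through.** No sample size, power, error rate or margin is involved, so the check sets the provisions side by side.

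**Step 1: the logic of the test.** All three criteria are required. An event that fails the second is outside the definition, whatever the answers on the first and third.

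**Step 2: what sample collection means here.** Section 8.1.7 uses the term for drawing the TNA blood sample at the early withdrawal visit. Nothing in the protocol or SAP extends it to vaccination. Section 9.2.2 judges the causality of adverse events against the investigational product. The two causality references in Section 9 therefore differ.

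**Step 3: a worked case.** Take a non-serious AESI, for example vitiligo or alopecia areata from Appendix B, in a vaccinated participant. Assume that it is judged unexpected, possibly caused by the vaccine, and a sign of greater risk than was known.
- Criterion 1 (unexpected): met, by assumption.
- Criterion 2 (related): not met as worded, because the blood or urine draw did not cause it.
- Criterion 3 (greater risk): met, by assumption.
- Result under Section 9.5: not an unanticipated problem.

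**Step 4: do other IRB routes catch that case?**
- Section 9.3.1: unexpected SAEs only. The case is non-serious.
- Section 9.4: pregnancy only.
- Section 11.6: protocol deviations, according to each IRB's requirements. No deviation has occurred.
- Section 13.2: serious adverse drug reactions and progress reports, if required. The case is not serious, and a progress report is not prompt notice.
- Sections 7.1 and 14: notice of study termination, of amendments, and of changes made to remove an immediate hazard. These follow a decision already taken.

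None of these routes sends the case promptly to the IRB.

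**Step 5: who does hear of it?** Section 9.3.1 sends potential AESIs to the sponsor's pharmacovigilance group within about 24 hours. Section 9.3.2 sends AESIs to FDA within 15 days. Section 8.4.1 sends potential AESIs to the DSMB. Section 9.2 has all adverse events recorded through Month 13, and Section 12.1 provides monthly data review. The missing recipient is the IRB.

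**Step 6: scope.** Planned injections are 3300 × 2 = 6600 of AV7909, 550 × 3 = 1650 of BioThrax and 3300 × 1 = 3300 of saline. The total is 6600 + 1650 + 3300 = 11,550. This is a planned maximum with no dropout. It shows how much of the intervention lies outside the causal clause and says nothing about how often a report would be missed.

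**The case against.** The best case for leaving the text alone is that a careful investigator would not read it narrowly. The criterion opens with study participation, the third criterion asks about risk from the study, the section defers to 45 CFR Part 46, and Section 13 binds the trial to applicable law. The wording that such problems are considered to include the listed events also leaves some room. On this view the effect is ambiguity rather than exclusion. That is a fair point. What the cited regulation requires cannot be checked from these documents. Even so, ambiguity in a reporting definition used at many sites is a reason to correct it, and the verb in the second criterion defines rather than illustrates.

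Four stronger readings are tempting and are not supported:
- **A reader might infer that vaccine-caused harm does not reach the IRB.** Unexpected SAEs do, under Section 9.3.1, and the SAE definition in Section 9.1.2 includes other medically significant events. Dosing and treatment-assignment errors are deviations under Section 11.6.
- **A reader might infer that the sponsor and CRO would be left uninformed.** Besides the routes in Step 5, suspected cold-chain loss leads to quarantine and contact with the CRO monitor (Section 6.2.2). Vials with discoloration or particles are quarantined and kept for collection (Section 6.2.3).
- **A reader might infer a contradiction with the section's remark that "some unanticipated problems involve social or economic harm instead of the physical or psychological harm associated with AEs".** It does not follow. Samples are tested for HIV, hepatitis and drugs of abuse (Section 8.3.2 and Table 7), so sampling itself could lead to social or economic harm.
- **A reader might take the 11,550 injections as a measure of harm.** They measure scope only.

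Some cross-references are off by one. Section 6.3.2 points to 9.5 for breaking the blind, which is in 9.6. Section 8.1.8 points to 9.6.2 for SAE and AESI follow-up, which is in 9.7.2. This fits a late insertion of Section 9.5 but does not prove where its wording came from.

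**Conclusion.** The definition is wrong as written. Its explanatory clause contradicts its own opening words and does not match the causality reference in Section 9.2.2. The consequence is limited to prompt IRB notification of unexpected, risk-raising problems that are neither SAEs nor deviations and that arise from the products, the injections or other study conduct. Endpoints, analysis populations, power and error control are unaffected.

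The conclusion rests on two assumptions: that sites apply the printed criteria, and that no local IRB policy or regulation asks for more than the protocol states. If either fails, the practical gap is smaller, but the inconsistency in the text remains. The correction is worth making because the rule concerns safety reporting and the change is small.

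**What to change.** In the second criterion of Section 9.5, replace the closing reference to sample collection so that the event may have been: *caused by participation in the study, including the investigational products (AV7909, BioThrax or placebo), any study procedure (sample collection among them), or the conduct of the study (blinding and data handling among them)*.

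Study conduct needs to be named. A clause limited to products and required procedures would not clearly cover a confidentiality breach or an accidental unblinding.

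The cost is one clause in a protocol amendment and possibly a few more IRB notifications. The SAP needs no change.

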9.6. Procedure for Breaking the Blind for Individual Subjects

In the case of a life-threatening emergency or pregnancy, the PI or designee may authorize unblinding of an affected participant in order to treat and ensure the safety of the participant. The PI will have 24-hour access to the IxRS for the purpose of unblinding and be trained in its use. IxRS access for unblinding will be set up for the PI to have sole access into IxRS for purposes of unblinding a participant and recording an unblinding event. Instructions to unblind treatment assignment within the IxRS system will be provided.

In the unlikely event that knowledge of the treatment assignment is necessary in order to treat or ensure the safety of a participant, PIs will make every effort to contact the study MMs (IQVIA MM and Emergent MM) prior to unblinding. This is not a mandatory requirement before unblinding, and in no way negates the PI's responsibility to make the final decision whether

unblinding is necessary. It is the PI's responsibility to inform the study MMs within 24 hours before unblinding to discuss the rationale for the unblinding; or if a study participant's treatment assignment is unblinded, the study MMs must be notified immediately, within 24 hours after the unblinding. The study MMs will immediately communicate instances of planned or unplanned unblinding with the Emergent Medical Officer (eg, within 24 hours of awareness of the situation).

In special circumstances, such as the occurrence of SUSARs or any safety signals, the study MMs in conjunction with the Emergent Medical Officer may also authorize unblinding for individual participants prior to database lock. It is not anticipated that all individual SAE reports will need to be unblinded. Additionally, the DSMB may recommend the unblinding of a particular participant (or participants) to the MM based on review of blinded data. The procedures for DSMB request to unblind participant(s) will be described in the DSMB Charter.

If a participant's study treatment assignment is unblinded for safety reasons, or if a participant becomes accidentally unblinded for any reason, the participant must (if applicable) be discontinued from receiving additional IP and will be requested to remain in the study for safety follow-up. Documentation of breaking the blind must be entered in the participant's source documents with the following information recorded: (1) date and time the blind was broken; (2) the rationale behind the unblinding decision/occurrence; (3) the names of the personnel involved; and (4) date/time of contact with the MM(s).

9.7. Follow-up of Adverse Events

All AEs/SAEs/AESIs will be followed until resolution, stabilization, or up to 30 days after the last study visit (Month 13).

9.7.1. Follow-up of Nonserious Adverse Events

Nonserious AEs that are identified on the last scheduled visit (Day 64 or EWV) must be recorded on the AE eCRF with the current status noted. All nonserious events that are ongoing at this time will be recorded as "Not Recovered/Not Resolved" on the AE eCRF. The status of ongoing, previously reported AEs will be reviewed at the Day 64/EWV to determine if resolved. For participants that continue in the study beyond Day 64, the status of ongoing AEs will be queried at the quarterly phone contacts to determine and update the resolution status in the AE eCRF and any new nonserious AEs will be collected until last phone follow-up (Month 13).

9.7.2. Follow-up of Serious Adverse Events or Adverse Events of Special Interest

This trial requires that participants be monitored for AEs/SAEs/AESIs up to Month 13. From Day 65 through Month 13, confirmed SAEs and confirmed (as assessed by the DSMB) AESIs will be recorded on the AE eCRF. The status of ongoing SAEs/AESIs after Day 64 will be reviewed at each quarterly safety phone contact to determine any new information and to update the resolution status in the AE eCRF.

The PI or designee will provide or arrange appropriate supportive care for participants for whom SAEs or potential AESIs are reported. Withdrawals of participants from vaccinations and/or the trial to treat SAEs/AESIs are at the discretion of the PI or designee, as subject to the guidance provided in [Section 7](#).

All SAEs/AESIs will be followed by the PI or designee until one or the other condition is met:

- The SAE/AESI is resolved or stable if expected to remain chronic.
- The participant is referred to a specialist or other physician for treatment and follow-up. The PI or designee will follow the participant's condition even if the participant is seen by another physician, to obtain information about the diagnosis and outcome and any treatments and medications administered for the event.

The following will be considered acceptable reasons for discontinuation of follow-up of ongoing SAEs/AESIs:

- Subject withdraws consent
- Subject is referred to appropriate long-term medical care
- Subject is considered lost to follow-up (refer to [Section 7.4](#) for description of contact attempts before a subject may be deemed lost to follow-up)

It is expected that the clinical site will obtain supporting medical records from appropriate physicians and record this information on the SAE/AESI Report Form (refer to [Section 9.3](#)) and AE eCRF. Additional information received related to any SAE/AESI must be forwarded within 24 hours of awareness to the Emergent Global PV Department.

10. STATISTICAL ANALYSIS

The statistical analysis plan (SAP) will be finalized prior to the enrollment of the first participant and will provide additional details on the statistical methods described below.

10.1. Sample Size and Power Considerations

Sample size for this study is based primarily on safety considerations. The total sample size across all three AV7909 groups is set at 3300 participants. Allowing a 10% drop-out rate, this sample size for safety (3000) is sufficient to detect, with 95% probability, an AE rate of 1:1000, or 0.1%.

It is expected that more participants will be excluded from the immunogenicity analysis population (Per Protocol [PP] Population; refer to [Section 10.2](#)) than excluded from the Safety Population. A 25% exclusion rate from the PP Population is assumed. Thus, the PP Population will include approximately 800 participants for each AV7909 group (2400 participants total) and 400 participants for the BioThrax group.

Even under the best manufacturing practices, between-lot variation exists and will be considered normal. It is assumed that the lot-to-lot geometric mean titer (GMT) ratio could be as low as 0.6 based on Emergent's experience with the BioThrax vaccine. Conservatively, the largest GMT ratio between two out of three lots is assumed to be 1.5. Assuming a coefficient of variation of 100% (slightly larger than the observed 91% in the phase 2 study, EBS.AVA.208), this study has >99% power to demonstrate lot consistency with the pre-specified equivalence bounds ([0.5, 2.0]) in terms of GMT ratio for TNA NF₅₀ at Day 64.

Based on the combined phase 1 and phase 2 data, the proportion of subjects receiving two doses of AV7909 on Day 1 and Day 15 with TNA NF₅₀ at Day 64 over 0.56 is approximately 63% with lower 95% CI of 50% (total n = 54). Even assuming a conservative 50%, the study provides >99% power of rejecting the null hypothesis of 40% in each of the three AV7909 lots and in the combined AV7909 group (three lots pooled).

For the non-inferiority endpoint, among subjects (n = 184) receiving BioThrax PEP regimen (3 doses, SC) in the EBS.AVA.006 study, 93.5% had TNA NF₅₀ values above 0.29 at Day 64. In the AV7909 phase 2 study (EBS.AVA.208), 86.5% of subjects (n = 37) had TNA NF₅₀ above 0.29 at Day 64. Assuming a rate of 93% for the BioThrax group and 83% for the AV7909 group, the sample sizes of 400 and 2400 provide approximately 98% power to demonstrate non-inferiority of the two-dose AV7909 IM regimen to the three-dose BioThrax SC regimen at Day 64 with a non-inferiority margin of 15%.

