10.5.1. Primary Immunogenicity Analysis

The primary immunogenicity endpoints will be tested in the hierarchy below. Testing of the next endpoint will only be carried out when all previous endpoints are met. According to the closed testing principle, this procedure ensures that the overall type I error rate is controlled at less than 5% and no additional adjustment is needed.

- 1a. AV7909 Lot Consistency Based on GMT Ratio of TNA NF₅₀ at Day 64:** the 95% CIs for the Day 64 TNA NF₅₀ geometric mean ratios between all three pairs of AV7909 groups (Lot 1 vs. Lot 2, Lot 2 vs. Lot 3, and Lot 1 vs. Lot 3) are within 0.5 and 2.0.
- 1b. AV7909 Lot Consistency Based on Protective Level of Immunogenicity at Day 64:** protective level of immunogenicity in all three consecutive AV7909 lots as demonstrated by the LB of the two-sided 95% CI to be $\geq 40\%$ for the proportions of AV7909 participants in each of the three lots achieving a TNA NF₅₀ ≥ 0.56 at Day 64.

The two endpoints 1a and 1b must both be met to demonstrate AV7909 lot consistency.

- 2a. AV7909 Immunogenicity at Day 64:** once lot consistency is demonstrated, the immunogenicity data on Day 64 will be pooled across all three AV7909 lots. AV7909 will be considered as achieving a protective level of immunity under the US FDA's Animal Rule at Day 64 if the LB for the two-sided 95% CI for the proportion of participants with TNA NF₅₀ values above the specified threshold of protection (≥ 0.56) is $\geq 40\%$.
- 2b. AV7909 Immunogenicity Based on Noninferiority vs BioThrax at Day 64:** the difference in the proportion of participants with TNA NF₅₀ values above the specified threshold of protection (≥ 0.29) will be calculated using the pooled AV7909 groups versus the BioThrax group. Noninferiority is demonstrated if the two-sided 95% lower CI of difference in proportions (AV7909 - BioThrax) is above -15%.

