2.4 Sample Size and Power Considerations

Sample size for this study is based primarily on safety considerations. The total sample size across all three AV7909 study groups is set at 3300 participants. Allowing a 10% drop-out rate, this sample size for safety (3000) is sufficient to detect, with 95% probability, an AE rate of 1:1000, or 0.1%.

It is expected that more participants will be excluded from the immunogenicity analysis population (Per Protocol [PP] Population; refer to [Section 3.2](#)) than excluded from the Safety Population. A 25% exclusion rate from the PP Population is assumed. Thus, the PP Population will include approximately 800 participants for each AV7909 group (2400 participants total) and 400 participants for the BioThrax group.

Even under the best manufacturing practices, between-lot variation exists and will be considered normal. It is assumed that the lot-to-lot geometric mean titer (GMT) ratio could be as low as 0.6 based on Emergent's experience with the BioThrax vaccine. Conservatively, the largest GMT ratio between two out of three lots is assumed to be 1.5. Assuming a coefficient of variation of 100% (slightly larger than the observed 91% in the phase 2 study, EBS.AVA.208), this study has >99% power to demonstrate lot consistency with the pre-specified equivalence bounds ([0.5, 2.0]) in terms of GMT ratio for TNA NF₅₀ at Day 64.

Based on the combined phase 1 and phase 2 data, the proportion of participants receiving two doses of AV7909 on Day 1 and Day 15 with TNA NF₅₀ at Day 64 over 0.56 is approximately 63% with lower 95% CI of 50% (total n = 54). Even assuming a conservative 50%, the study provides >99% power of rejecting the null hypothesis of 40% in each of the three AV7909 lots and in the combined AV7909 group (three lots pooled).

For the non-inferiority endpoint, among participants (n = 184) receiving BioThrax PEP regimen (3 doses, SC) in the EBS.AVA.006 study, 93.5% had TNA NF₅₀ values above 0.29 at Day 64. In the AV7909 phase 2 study (EBS.AVA.208), 86.5% of participants (n = 37) had TNA NF₅₀ above 0.29 at Day 64. Assuming a rate of 93% for the BioThrax group and 83% for the AV7909 group, the sample sizes of 400 and 2400 provide approximately 98% power to demonstrate non-inferiority of the two-dose AV7909 IM regimen to the three-dose BioThrax SC regimen at Day 64 with a non-inferiority margin of 15%.

The sample size calculation was performed using PROC POWER in SAS/STAT 9.4.

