4.8 Multiplicity Adjustment

The primary immunogenicity endpoints will be tested in the hierarchy below. Testing of the next endpoint will only be carried out when all previous endpoints are met. According to the closed testing principle, this procedure ensures that the overall type I error rate is controlled at less than 5% and no additional adjustment is needed.

- 1a. AV7909 Lot Consistency Based on GMT ratio of TNA NF₅₀ at Day 64:** the 95% CIs for the Day 64 TNA NF₅₀ geometric mean ratios between all three pairs of AV7909 groups (Lot 1 vs. Lot 2, Lot 2 vs. Lot 3, and Lot 1 vs. Lot 3) are within 0.5 and 2.0.
- 1b. AV7909 Lot Consistency Based on Protective Level of Immunogenicity at Day 64:** protective level of immunogenicity in all three consecutive AV7909 lots as demonstrated by lower bound (LB) of the two-sided 95% CI $\geq 40\%$ for the proportion of AV7909 participants in each of the three lots achieving a TNA NF₅₀ ≥ 0.56 at Day 64.

Together, the two endpoints **1a** and **1b** must both be met to demonstrate AV7909 lot consistency.

- 2a. AV7909 Immunogenicity at Day 64:** once lot consistency is demonstrated, the immunogenicity data on Day 64 will be pooled across all three AV7909 lots. AV7909 will be considered as achieving a protective level of immunity under the US FDA's Animal Rule at Day 64 if the LB for the two-sided 95% CI for the proportion of participants with TNA NF₅₀ values above the specified threshold of protection (≥ 0.56) is $\geq 40\%$.
- 2b. AV7909 Immunogenicity Based on Non-inferiority vs BioThrax at Day 64:** the difference in the proportion of participants with TNA NF₅₀ values above the specified threshold of protection (≥ 0.29) will be calculated using the pooled AV7909 groups versus the BioThrax group. Non-inferiority is demonstrated if the two-sided 95% lower CI of difference in proportions (AV7909 minus BioThrax) is above -15%.

Once all the primary endpoints (AV7909 lot consistency and immunogenicity) are satisfied, the secondary immunogenicity endpoint, AV7909 immunogenicity at Day 29, will be considered appropriately immunogenic under the US FDA's Animal Rule on Day 29 if the LB for the two-sided 95% CI for the proportion of participants pooled from all three AV7909 groups with TNA NF₅₀ values above the specified threshold of protection (≥ 0.15) is $\geq 67\%$.

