6.2.2 AV7909 Immunogenicity

6.2.2.1 AV7909 Immunogenicity at Day 64

The immunogenicity of AV7909 on Day 64 will be assessed by the proportion of participants pooled across all three AV7909 lots with TNA NF₅₀ values ≥ 0.56 on Day 64. The proportion and two-sided 95% CI (exact Clopper-Pearson confidence limits) for the proportion will be provided for the combined AV7909 group (three lots pooled). AV7909 will be considered as achieving a protective level of immunogenicity at Day 64 if the LB of the two-sided 95% CI of the proportion is $\geq 40\%$.

6.2.2.2 AV7909 Immunogenicity Based on Non-inferiority vs BioThrax at Day 64

Non-inferiority of AV7909 versus BioThrax on Day 64 is satisfied if the LB for the two-sided 95% lower CI of the difference (AV7909 - BioThrax) in the proportion of participants with TNA NF₅₀ values ≥ 0.29 in the combined AV7909 group (three lots pooled) versus BioThrax group is $> -15\%$.

The within-group proportions and the associated two-sided 95% CIs (exact Clopper-Pearson confidence limits) will be provided for the combined AV7909 group (three lots pooled) and

BioThrax group. The treatment difference in proportion between the combined AV7909 group and BioThrax group and two-sided 95% lower CI will be calculated using Newcombe score method.

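### Is the stated power of approximately 98% for the non-inferiority comparison with BioThrax wrong, given that the planned Newcombe rule yields about 96%?

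*Protocol*

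**What the plan says.** Protocol 10.1 gives the planning assumptions for endpoint 2b, the proportion with TNA NF50 at or above 0.29 on Day 64: "Assuming a rate of 93% for the BioThrax group and 83% for the AV7909 group". It continues that "the sample sizes of 400 and 2400 provide approximately 98% power to demonstrate non-inferiority" "with a non-inferiority margin of 15" percent. The Protocol Synopsis and SAP 2.4 carry the same figure. The sizes are per-protocol counts after an assumed 25% exclusion.

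The success rule is in Protocol 10.5.1: "the two-sided 95% lower CI of difference in proportions (AV7909 - BioThrax) is above -15" percent. SAP 4.8 repeats it. SAP 6.2.2.2 names the interval: the difference and its "two-sided 95% lower CI will be calculated using Newcombe score method".

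On how power was obtained, SAP 2.4 says only this: "The sample size calculation was performed using PROC POWER in SAS/STAT 9.4". Neither document gives the test option or the alpha used. Protocol 10.1 also states what drives enrolment: "Sample size for this study is based primarily on safety considerations".

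**The concern.** All the ingredients of the power figure are in the documents: two rates, two sample sizes, a margin, a confidence level and an interval method. A reader can therefore recompute it, and the result is 96.4%, not 98%. Other common methods at the same confidence level come out lower still.

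Endpoint 2b is a primary endpoint in a study meant to support licensure, and the secondary Day 29 endpoint is tested only if 2b succeeds. Read as a risk of failure, the gap looks larger: a 3.6% chance of missing the endpoint at the planning rates, against an implied 2%. A gap of this kind could also mean that power was worked out at a looser error level than the one used to judge the result.

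**Working it through.** **Inputs.** From Protocol 10.1: AV7909 rate 0.83 with n = 2400; BioThrax rate 0.93 with n = 400; margin 0.15. From Protocol 10.5.1 and SAP 4.8: lower limit of a two-sided 95% interval, so z = 1.96 (one-sided 0.025). From SAP 6.2.2.2: Newcombe score interval.

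**The rule.** For an observed proportion p out of n, the Wilson limits are

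(p + z²/2n ± z·√[p(1−p)/n + z²/4n²]) / (1 + z²/n).

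With l₁ the lower Wilson limit for AV7909 and u₂ the upper one for BioThrax, the Newcombe lower limit for the difference is

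L = (p₁ − p₂) − √[(p₁ − l₁)² + (u₂ − p₂)²].

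If the observed rates equal the planning rates, l₁ = 0.8144 and u₂ = 0.9511. Then L = −0.10 − √(0.0156² + 0.0211²) = −0.126, clear of −0.15.

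**Power under the rule.** Sum the binomial probabilities of all pairs of counts (2400 at 0.83; 400 at 0.93) for which L > −0.15. The result is 0.9637. A simulation of 200,000 trials gives 0.9643. The distance from the stated figure is 98 − 96.4 = 1.6 points.

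**How firm the inputs are.** A 25% exclusion leaves 3300 × 0.75 = 2475 and 550 × 0.75 = 412.5; the plan rounds down to 2400 and 400. The rates are whole percentages chosen for planning. The same Newcombe rule gives:

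| AV7909 / BioThrax n | AV7909 rate | BioThrax rate | Power |
|---|---|---|---|
| 2400 / 400 | 83% | 93% | 96.4% |
| 2475 / 412 | 83% | 93% | 96.8% |
| 2400 / 400 | 83.4% | 93% | 98.3% |
| 2400 / 400 | 83% | 92.6% | 97.9% |
| 2400 / 400 | 83.2% | 92.8% | 98.1% |
| 2400 / 400 | 83% | 93.5% | 93.3% |
| 2400 / 400 | 86.5% | 93.5% | over 99.9% |

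The last row uses the rates that Protocol 10.1 reports from earlier studies. Changes of less than half a point in a planning rate move power by as much as the gap in question, in either direction.

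**Other methods at one-sided 0.025, 2400 and 400.** Newcombe with continuity correction gives 95.8%. The score test with restricted variance gives 96.1% by enumeration and 95.5% by the Farrington-Manning formula. The Wald interval gives 94.4% by enumeration. For the unpooled normal approximation, SE = √(0.83·0.17/2400 + 0.93·0.07/400) = 0.01488, and Φ(0.05/0.01488 − 1.96) = 0.919. None of these is the planned analysis, so they say little about the chance of success in this trial.

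**At one-sided 0.05.** Newcombe gives 98.1%; the score test gives 98.0% by enumeration and 97.5% by formula. These come closest to the stated figure at the stated inputs.

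**The case for a change.** The strongest case is this. No method tried at the plan's own error level reaches 98% with the stated inputs, and the Newcombe rule is the most favourable of them. Removing the rounding of the sample sizes recovers only 0.4 of the 1.6 points. The failure risk is 3.6/2 = 1.8 times what is implied. A true 98% at the same 1:6 ratio would need about 460 and 2760 per-protocol participants, 15% more than planned. The near-match at one-sided 0.05 suggests that power and decision rule may have used different error levels.

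The arithmetic in this stands: 96.4% is correct for the planned rule at the stated inputs. It also stands that SAP 2.4 names the software without the test option or alpha.

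The inference to an error does not follow. The one-sided 0.05 explanation fits, but a fit is not evidence of what was run, and nothing in the documents bears on it. Power is often computed with a different approximation from the final interval, so a mismatch with Newcombe enumeration is not in itself a mistake. The 460 and 2760 needed for 98% would also arise within the planned enrolment if per-protocol exclusion were 1 − 2760/3300 = 16.4% instead of the assumed 25%. The figure is thus no firmer than the exclusion assumption behind it.

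The sensitivity argument has its own limit. The rates are planning choices, not rounded measurements, and a small shift the other way lowers power to 93.3%. It shows that a difference of 1.6 points carries little information, not that 98% is the exact answer.

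**Conclusion.** The concern does not hold. The planned two-sided 95% Newcombe rule gives 96.4% at 2400 and 400, which is within two points of a figure stated as approximate. Two points is a convention for judging such agreement and not something in the plan, but it is reasonable here because sub-point changes in the assumed rates move power by as much.

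The gap has no consequence. Enrolment rests primarily on safety, and power above 96% is ample. The AV7909 planning rate of 83% is already below the 86.5% seen in phase 2. Margin, error rate, interval method and testing order would be the same with either figure. Recording the PROC POWER option and alpha would make the calculation traceable, but its absence does not show that the figure is wrong.

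This conclusion assumes the Newcombe interval without continuity correction and independent binomial counts at the planning rates. Evidence that power had been computed at one-sided 0.05 would establish a mismatch with the decision rule, but power under that rule would still be 96.4%.
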